9.2.2. Exclusion criteria

There are no exclusion criteria for this study.

9.3. Variables

The main variables included in the study are the following:

Table 1. List of variables

Variable	Role	Data source(s)	DBCG variable(s)
Diagnosis (ICD-10 code: DC50)	Exposure/Inclusion	DBCG registry	Not applicable
Treatment with palbociclib	Exposure/Inclusion	DBCG registry	RE201, RE201A
Date of birth	Baseline characteristic	DBCG registry	Based on M1
Date of breast cancer diagnosis	Baseline characteristic	DBCG registry	Not applicable
Occurrence of metastases	Baseline characteristic	DBCG registry	RE220-RE227
Type of metastases (visceral vs non-visceral)	Baseline characteristic	DBCG registry	RE220-RE227
Number of metastases sites	Baseline characteristic	DBCG registry	RE220-RE227
Location of metastases	Baseline characteristic	DBCG registry	RE10-18 + 80-81, 117-119, 219-222
Surgery	Baseline characteristic	DBCG registry	RE19
De Novo (primary MBC)	Baseline characteristic	DBCG registry	Calculated
Breast cancer disease duration – median time from initial breast cancer diagnosis (incidence date) to relapse	Baseline characteristic	Estimated via DBCG registry registrations	Based on variables listed in this table
Date of relapse	Baseline characteristic	DBCG registry	RE1-RE3
Date for treatment initiation with palbociclib	Baseline characteristic	DBCG registry	RE203-RE205
Date for treatment stop with palbociclib	Baseline characteristic	DBCG registry	RE206-RE208
Post-palbociclib treatment (first subsequent treatment post-palbociclib)	Baseline characteristic	DBCG registry	RE24, RE24A, RE33, RE33A, RE42, RE42A, RE69, RE69A
Reasons to discontinuation with palbociclib	Baseline characteristic	DBCG registry	RE209, RE209A
Death date	Baseline characteristic	DBCG registry	Not applicable
PFS (see section 8.1 for definition)	Outcome	Estimated via DBCG registry	Based on variables listed in this table
ToT with palbociclib (see section 8.1 for definition)	Outcome	Estimated via DBCG registry registrations	Based on variables listed in this table
OS (see section 8.1 for definition)	Outcome	Estimated via DBCG registry registrations	Based on variables listed in this table (overall and after 6, 12 and 24 months of palbociclib treatment (landmark times))

9.4. Data sources

This study will be based solely on the DBCG registry. No other Danish healthcare registries will be included. The DBCG registry also includes information on death.

9.5. Study size

It is estimated that the total population of palbociclib-treated patients with HR+/HER2- locally advanced or metastatic breast cancer included in the DBCG registry constitutes of 1,500 patients since the introduction of palbociclib in Denmark (from 01 January 2017 to 31 December 2020).

9.5.1. Sub-groups

In addition, the primary objective (PFS, ToT) as well as some of the secondary objectives (OS and first subsequent post-palbociclib treatment) will be addressed for the following sub-groups such as those below provided sample size is sufficient:

- Specific age groups (below 50 years, 50 -70, and above 70 years of age)
- Patients with visceral disease (defined as metastases in the organs, eg, lung, liver)

9.6. Data management

The Danish Breast Cancer Group hosts the DBCG registry and all analyses will be performed by DBCG's biostatistical researchers following this protocol and a pre-specified SAP. Pfizer will not have access to data at the individual level – only summary data in tables produced by DBCG as part of the discussion of results and reporting.

The individual-level patient data in the registry are well-structured, of high quality, and in a ready-to-analyse format. Data will be analysed using SAS software.

9.7. Data analysis

In general, some research questions will be addressed via descriptive statistics, including stratification on sub-groups. In the PFS and OS analyses, Kaplan-Meier survival distribution functions will be estimated, implying that statistics on median survival expectedly will be available. Overall survival will be estimated for all patients with a censoring of data by 01 May 2022, ie, why the maximum follow-up period for the first treated palbociclib patient 01 January 2017 will be close to 5.5 years. In Kaplan-Meier landmark analyses OS will furthermore be analysed and reported after 6, 12 and 24 months from treatment initiation.

A separate SAP, including shell tables, will be developed prior to data analysis. The SAP will be dated, filed, and maintained by the sponsor. The SAP will also include precise definitions of the sub-groups. The SAP may modify the plans outlined in the protocol; any major modifications of primary endpoint definitions or their analyses would be reflected in a protocol amendment.

9.8. Quality control

DBCG's biostatistical researchers will compile the full data set and perform the analyses. The researchers will follow generally accepted methods as well as DBCG's internal guidelines for data analysis.

The study involves analyses of individual data. DBCG's biostatistical researchers will, however, only have access to data in de-personalized form (by encrypted personal identification codes). Pfizer will not have access to any individual data in the project, only the summary data produced by DBCG's biostatistical researchers.

Furthermore, the study design, literature, decisions on data analysis, interpretation of the results of the study, as well as reporting (manuscript) will be only discussed in the project group (see list of responsible parties in section 3).

The study though will as a Non-Interventional Study with Pfizer as sponsor, collaborator and part of the project group have to use certain templates, incl. the present protocol template and a template for the SAP, etc. Furthermore, the study has to follow certain review stages by the sponsor such as a technical protocol review and a review of the final scientific manuscript prior to submission to a scientific journal.

9.9. Strengths and limitations of the research methods

Naturally, this study has both strengths and limitations.

DBCG has provided a long history of compiling and maintaining registry data since the past 40 years. The data from DBCG has been part of both national and international studies. In addition the data collected by DBCG have been published in more than 430 peer-reviewed papers (27).

And has been part of several meta-analyses conducted by Early Breast Cancer Trialists' Collaborative Group (28-29). The extension of this registry to include relapsed patients nationwide is therefore a very unique feature of this registry. To collect relapse data about MBC patients has been a challenge in many countries.

The DBCG registry holds the most detailed and comprehensive information about patients diagnosed with HR+/HER2- locally advanced or metastatic breast cancer, implying that, compared to other Danish healthcare registries, new and more detailed results can be presented. Furthermore, the study is a study carried out at the population level, which makes the study and its results as complete and generalizable as possible and minimizes the risk of selection bias.

At the same time, since this study only involves data from the DBCG registry, the completion and validity of the analyses rely 100% on the quality and validity of the data in the registry.

The study does furthermore only include the data available in the DBCG registry and only data of a quantitative nature. More qualitative data and outcomes following the treatment of the breast cancer patients will though not be included.

9.10. Other aspects

Not applicable.

10. PROTECTION OF HUMAN SUBJECTS

All parties will ensure protection of patient personal data and will not include patient names on any sponsor forms, reports, or publications, or in any other disclosures except where required by law. As described, DBCG's biostatistical researchers will have access only to data in de-personalized form (encrypted personal identification codes (CPR)). Pfizer will not have access to any individual data in connection with the project but only the summary data produced by DBCG's biostatistical researchers.

10.1. Patient information

This study involves data that exist in anonymized structured format and contain no patient personal information.

10.2. Patient consent

As this study involves anonymized structured data, which according to applicable legal requirements do not contain data subject to privacy laws, obtaining informed consent from patients by Pfizer is not required.

10.3. Institutional review board (IRB)/Independent ethics committee (IEC)

Approval from the Danish Data Protection Agency is not necessary for this type of study. However, in accordance with General Data Protection Regulation (GDPR) the study will be reported via Pactius to the Capital Region of Denmark's research list.

Approval from an ethics committee is not required by Danish law since a retrospective database study does not involve collection of or research on biological material.

No other approvals from IRBs or IECs are necessary under Danish law.

10.4. Ethical conduct of the study

The study will be conducted in accordance with legal and regulatory requirements, as well as with scientific purpose, value, and rigor, and will follow generally accepted research practices described Good practices for real-world data studies of treatment and/or

comparative effectiveness: Recommendations from the joint ISPOR-ISPE Special Task Force on real-world evidence in health care decision making (30).

11. MANAGEMENT AND REPORTING OF ADVERSE EVENTS/ADVERSE REACTIONS

This study involves data that exist as structured data by the time of study start or a combination of existing structured data and unstructured data, which will be converted to structured form during the implementation of the protocol solely by a computer using automated/algorithmic methods, such as natural language processing.

In these data sources, individual patient data are not retrieved or validated, and it is not possible to link (ie, identify a potential association between) a particular product and medical event for any individual. Thus, the minimum criteria for reporting an adverse event (AE) (ie, identifiable patient, identifiable reporter, a suspect product, and event) cannot be met.

12. PLANS FOR DISSEMINATING AND COMMUNICATING STUDY RESULTS

Besides a study report presenting the results, a manuscript for a scientific article will be written and submitted to an international peer-reviewed journal. Authorship of the article manuscripts will follow the requirements set by the International Committee of Medical Journal Editors (ICMJE) (<http://www.icmje.org/recommendations/browse/roles-and-responsibilities/defining-the-role-of-authors-and-contributors.html>). All members of the project group as described in section 3 of this protocol, including external members and Pfizer employees, fulfilling these requirements with respect to the article manuscripts are offered co-authorship of the scientific article.

The study and its results will also be disclosed at the ClinicalTrials.gov website.

In the event of any prohibition or restriction imposed (eg, clinical hold) by an applicable competent authority in any area of the world, or if the party responsible for collecting is aware of any new information which might influence the evaluation of the benefits and risks of a Pfizer product, Pfizer should be informed immediately.

14. LIST OF TABLES

Table 1. List of variables (see section 9.3).

15. LIST OF FIGURES

Not applicable.

ANNEX 1. LIST OF STAND ALONE DOCUMENTS

Not applicable.

ANNEX 2. ADDITIONAL INFORMATION

Not applicable.

## 1 AMENDMENTS FROM PREVIOUS VERSION(S)

Not applicable.

## 2 INTRODUCTION

*The discovery and development of CDK (cyclin-dependent kinases) 4/6 inhibitors have revolutionised the paradigm of therapeutic management of hormone receptor-positive (HR+) metastatic breast cancer (MBC) worldwide. The most common cancer globally is breast cancer [1]. In Denmark, breast cancer is the most frequent cancer in women, with approximately 4,700 new cases per year; and the 5-year OS is estimated to be 86%. Currently, approx. 64,000 women are living with a breast cancer diagnosis. It is estimated that approx. 20% of the patients initially diagnosed with breast cancer will at some stage in their life experience a relapse of the disease (loco-regional or distant metastasis). The median OS of metastatic breast cancer is between 2-3 years; however, 25% of the patients can attain an OS of 5 years. The incidence of loco-regional or metastatic HR+/Human epidermal growth factor receptor 2-negative (HER2-) breast cancer in Denmark is estimated to be around 500 patients yearly [2]..*

[figure not shown]
*The first cell-cycle inhibitor was palbociclib, which was approved by the FDA on the basis of the phase 2 study PALOMA-1 [3]. This study showed doubling of the PFS from 10.2 to 20.2 months when a combination of palbociclib and letrozole was given to the HR+/HER2-advanced breast cancer patients. These significant results were later confirmed in the phase 3 study PALOMA-2 as well [4]. This approval was followed by the other two CDK4/6 inhibitors ribociclib and abemaciclib. In Denmark, these targeted therapeutic agents were incorporated into the clinical practice from 2016 onwards [5]. The introduction of CDK4/6 inhibitors has permanently transformed the therapeutic management of HR+ MBC worldwide. The three CDK4/6 inhibitors palbociclib, ribociclib, and abemaciclib are approved for either with a combination of aromatase inhibitor (AI) or with fulvestrant.*

### 2.1 STUDY RATIONALE

*To date, several Phase II and III randomised controlled trials (RCTs) have evaluated CDK4/6 inhibitors in the treatment of HR+/HER2- advanced breast cancer/MBC. Randomisation and blinding are considered to be the gold standard for determining the effect of a treatment in randomised controlled clinical trials. However, due to strict protocol-specified definition of inclusion criteria, populations in the randomised trials do not always represent patients treated in clinical practice. Therefore, real-world data (RWD) are increasingly being used to understand the safety and effectiveness of new drug regimens in actual clinical practice where patient populations are heterogeneous[6,7].*

*However, there is a need for additional and updated real-world evidence (RWE) about the CDK4/6 inhibitors in a real-world setting. Most RWE studies on CDK4/6 inhibitors published to date are studies conducted in the USA. Hence, there is a need for*

PFIZER CONFIDENTIAL

*national/European data for CDK4/6 inhibitors in the treatment of HR+/HER2- advanced breast cancer/MBC.*

*In Denmark, access to the Danish Breast Cancer Group (DBCG) clinical register is unique and feasible. Thus, collecting clinical and pathological data from patients from all regions of Denmark will add on to the existing clinical evidence. The project aims to collect retrospective clinical effectiveness data and treatment pattern data on palbociclib.*

*Compared to existing RWE studies, this study will, through its access to the national DBCG clinical register, allow us to analyse patient data for a total country population with no selection bias, as all patients are included. Thus, collecting clinical and pathological RWD from patients from all regions of Denmark via the DBCG register will add on to the existing pool of RWE.*

*Thus, the overall objective is to use data from the Danish DBCG register to retrospectively describe and assess clinical and demographical characteristics and treatment patterns in a real-world setting of patients with HR+/HER2- locally advanced or metastatic breast cancer receiving palbociclib in combination treatment.*

Note: in this document, any text taken directly from the non-interventional (NI) study protocol is *italicised*.

## 2.2 STUDY DESIGN

*The study is designed as a secondary data collection Non-Interventional Study (NIS) based on retrospective data from the DBCG clinical register. The study is a single-arm study focusing only on patients treated with palbociclib in Denmark.*

### **Study population**

*Patients registered in the DBCG register with HR+/HER2- locally advanced or metastatic breast cancer and treated with palbociclib (first- or second-line) (1 January 2017 to 31 December 2020).*

*It is estimated that the total population included in the DBCG register consists of 1,500 patients in Denmark.*

### **Data source**

*The entire study will be undertaken among patients registered in the DBCG clinical register. That is, the study will be based solely on the DBCG register. No other Danish healthcare registers will be included. The DBCG register also includes information on death.*

*Since its establishment in 1976, the DBCG has maintained a clinical register for early breast cancer patients in Denmark in which surgeons, pathologists, medical geneticists and oncologists report data regarding diagnosis, treatment and follow-up of breast cancer. This is a unique clinical register. This well-established breast cancer register*

PFIZER CONFIDENTIAL

(1976) managed by DBCG was expanded in 2017 to include retrospective and prospective clinical and pathological data on breast cancer patients with a relapse. This includes both the primary MBC (De Novo) and recurrent MBC.

The DBCG register focusing on relapses, which the study will be based on, is one of several DBCG registries. It is estimated that by the end of 2021, the DBCG register will include all Danish patients with locally advanced or metastatic breast cancer. The data and records in the register are based on systematic review following a standard case report form of all electronic patient records of patients diagnosed with locally advanced or metastatic breast cancer.

The data collection and the ongoing population of the DBCG register are performed by healthcare professionals in the DBCG secretariat and are conducted independently of this study. Compared to other exhaustive national Danish patient registries, the DBCG register contains detailed clinical and pathological data about the treatment patterns of patients with HR+/HER2- locally advanced or metastatic breast cancer.

### **Treatment/cohort labels**

As stated, this study focuses only on the cohort of patients with HR+/HER2- locally advanced or metastatic breast cancer treated with palbociclib.

### **2.3 STUDY OBJECTIVES**

*In general, the overall objective is to use data from the Danish DBCG register to retrospectively describe and assess clinical and demographical characteristics and treatment patterns in a real-world setting of patients with HR+/HER2- locally advanced or metastatic breast cancer receiving palbociclib in combination treatment. The project will include both first- and second-line patients.*

*The primary objective is to estimate*

- Progression-Free Survival (PFS) and
- Time on Treatment (ToT)

*of patients receiving Palbociclib in combination with aromatase inhibitor (AI).*

Details regarding primary and secondary endpoints are described in section 5.

### **3 HYPOTHESES AND DECISION RULES**

*The study is purely descriptive and explorative. No formal hypotheses will be tested in the study.*

PFIZER CONFIDENTIAL

## 4 ANALYSIS SETS/POPULATIONS

*As stated, this study includes the population of patients with HR+/HER2- locally advanced or metastatic breast cancer treated with palbociclib identified in the DBCG register.*

The inclusion and exclusion criteria are specified below.

### **Inclusion criteria**

*To be eligible for inclusion in the study, patients must meet the following criteria:*

- *Patients with breast cancer (ICD10: DC50)*
- *A diagnosis of HR+/HER2- locally advanced or metastatic breast cancer*
- *Initiated treatment with palbociclib as either 1st or 2nd line treatment between 01 January 2017 and 31 December 2020*
- *Inclusion date: Date of relapse/stage IV disease/progression leading to initiation of palbociclib+AI/progression leading to initiation of palbociclib+fulvestrant*

### **Exclusion criteria**

*There are no exclusion criteria for this study.*

## 4.1 SUBGROUPS

*For the population of patients with HR+/HER2- locally advanced or MBC treated with palbociclib, results will also be presented for the following subgroups:*

- *Patients younger than 50 years*
- *Patients aged 50-70 years*
- *Patients older than 70 years*
- *Patients with visceral disease (defined as metastases in the organs, e.g., lung, liver)*
- *Patients without visceral disease (defined as metastases in the organs, e.g., lung, liver)*

## 5 ENDPOINTS AND VARIABLES

[figure not shown]
*The primary endpoints of the study are:*

- *Progression-Free Survival (PFS) of patients receiving palbociclib in combination with aromatase inhibitor (AI)*
- *Time on Treatment (ToT) of patients receiving palbociclib in combination with AI*

*The secondary endpoints are:*

- *PFS of patients receiving palbociclib in combination with Fulvestrant*
- *ToT with palbociclib in combination with Fulvestrant*
- *Overall Survival (OS) in patients receiving palbociclib in combination with AI*
- *Overall Survival (OS) in patients receiving palbociclib in combination with Fulvestrant*
- *First subsequent post-palbociclib treatment upon progression*

PFIZER CONFIDENTIAL

- *Results in terms of disease-specific descriptive statistics describing the patients who have received Palbociclib:*
  - *Type, number and location of metastases (visceral vs. non-visceral)*
  - *Surgery*
  - *Type and number of adjuvant treatment(s)*
  - *De novo (primary MBC)*
  - *Recurrent MBC*
  - *Median time from initial breast cancer diagnosis (incidence date) to relapse (only relevant for recurrent MBC)*

## 5.1 VARIABLES

*The main variables included in the study are the following:*

**Table 1.** List of variables

Variable	Role	Data source(s)	DBCG variable(s)
Diagnosis (ICD10 code: DC50)	Exposure/Inclusion criteria	DBCG register	-
Treatment with palbociclib	Exposure/Inclusion criteria	DBCG register	RE201, RE201A
Date of birth	Baseline characteristic	DBCG register	Based on M1
Date of breast cancer diagnosis	Outcome	DBCG register	-
Occurrence of metastases	Characteristics	DBCG register	RE220-RE227
Type of metastases	Characteristics	DBCG register	RE220-RE227
Number of metastases sites	Characteristics	DBCG register	RE220-RE227
Location of metastases	Characteristics	DBCG register	RE10-18 + 80-81, 117-119, 219-222
Surgery	Characteristics	DBCG register	RE19
De Novo (primary MBC)	Characteristics	DBCG register	Calculated
Breast cancer disease duration – median time from initial breast cancer diagnosis (incidence date) to relapse	Estimated outcome	Estimated via DBCG register registrations	Based on variables listed in this table
Date of relapse	Outcome	DBCG register	RE1-RE3
Date for treatment initiation with palbociclib	Outcome	DBCG register	RE203-RE205

PFIZER CONFIDENTIAL

Date for treatment stop with palbociclib	Outcome	DBCG register	RE206-RE208
Time on Treatment (ToT) with Palbociclib	Estimated outcome	Estimated via DBCG register registrations	Based on variables listed in this table
Reasons to discontinuation with palbociclib	Outcome	DBCG register	RE209, RE209A
Progression Free Survival (PFS)	Estimated outcome	Estimated via DBCG register registrations	Based on variables listed in this table
Post-palbociclib treatment (first subsequent treatment post-palbociclib)	Outcome	DBCG register	RE24, RE24A, RE33, RE33A, RE42, RE42A, RE69, RE69A
Death date	Outcome	DBCG register/Danish Cause of Death Register	-
Overall Survival (OS)	Estimated outcome	Estimated via DBCG register registrations	Based on variables listed in this table

## 6 HANDLING OF MISSING VALUES

The study will only include patients for whom there are complete registrations in the DBCG register. Thus, decisions on handling of missing values is not relevant.

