A comprehensive retrospective observational analysis of electronic health records within the Flatiron Health Analytic Database was carried out with palbociclib (26). A total of 1430 patients with ≥ 3 months of follow-up received palbociclib plus letrozole or letrozole alone in the first-line setting between 03 February 2015, and 28 February 2019. Real-world PFS and OS were analyzed. The results showed that plus letrozole was associated with longer PFS than letrozole alone in a heterogeneous population and among various patient subgroups. In the adjusted analysis to balance patient characteristics between arms, palbociclib combination treatment was associated with significantly longer median PFS compared to letrozole alone (20.0 vs 11.9 months; HR, 0.58; 95% confidence interval [CI], 0.49–0.69; $P < 0.0001$). These results complement the results from the randomized Phase 3 study PALOMA-2 where the hazard ratio was = 0.58 (95% CI: 0.46–0.72; two-sided $P < 0.001$) (26).

Compared to existing RWE studies the present study will with access to the national DBCG clinical registry allow us to analyse patient data for a total country population with no selection bias as all patients are included. Thus collecting clinical and pathological RW data from patients from all regions of Denmark via the DBCG registry will add on to the existing pool of RWE.

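### SAP section 6 admits only patients with undefined complete registrations: an unlisted exclusion that conflicts with the stated absence of exclusion criteria and that no planned table would count

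*SAP*

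**What the plan says.** SAP section 6 has two sentences. The first is "The study will only include patients for whom there are complete registrations in the DBCG register". The second draws the consequence: "Thus, decisions on handling of missing values is not relevant". Neither document defines a complete registration.

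SAP section 4 lists four inclusion conditions (diagnosis code, HR+/HER2- disease, palbociclib start window, inclusion date). Completeness is not among them, nor is it in protocol 9.2.1. Under exclusion criteria the SAP says "There are no exclusion criteria for this study", and protocol 9.2.2 agrees. SAP 2.1 says that the register will "allow us to analyse patient data for a total country population with no selection bias, as all patients are included"; protocol section 7 makes the same claim.

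On register coverage, SAP 2.2 says "It is estimated that by the end of 2021, the DBCG register will include all Danish patients with locally advanced or metastatic breast cancer".

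The shells in SAP section 8 start from included patients, with Table 2 setting them at 100%. Tables 2 to 7 have no row for patients identified, dropped or with an unknown value.

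ToT is defined in SAP 7.1 and protocol 8.1 only as palbociclib start to palbociclib stop. SAP 7.2 plans Kaplan-Meier for it. PFS has a censoring date in both documents (31 December 2020) and OS has one in the protocol (01 May 2022). ToT has none.

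**The concern.** Unless every eligible patient has a complete registration, three statements cannot all be true: only complete registrations enter, there are no exclusion criteria, and all patients are included. The rule that decides who is analysed stands only in a missing-data paragraph, and it depends on an undefined word. Different readings of that word can give different analysed sets for both primary endpoints, PFS and ToT in the AI combination.

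The study is descriptive, so who is described is central to the result. Protocol 9.9 says that validity rests entirely on register quality, yet no planned output would show that quality. A reader of the report could not tell whether the restriction removed nobody or a tenth of the cohort, and would meanwhile be told that there is no selection bias.

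**Working it through.** There is no plan figure to reproduce. The 1,500 in SAP 2.2 and protocol 9.5 is a register estimate without a derivation. The check has a textual part and a sizing part.

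**What complete could mean**

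- *Every Table 1 variable filled.* This cannot be intended. Table 1 includes the death date and "Date for treatment stop with palbociclib", which living patients and patients still on treatment do not have. Time from diagnosis to relapse applies only to recurrent disease (SAP section 5). Kaplan-Meier (SAP 7.2) and the allowance for no subsequent treatment (note to Table 7) also point against it.
- *A named subset of variables filled.* This is possible, but no subset is named.
- *Register review of the patient's record finished.* This is plausible. The register is filled from a standard case report form, and full coverage was expected by the end of 2021.

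The last two readings give different sets whenever a finished record still has a gap in a required field.

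**Number dropped (all rates assumed)**

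Take six baseline field groups: birth date, diagnosis date, the metastasis fields RE220-RE227, location of metastases, surgery (RE19) and palbociclib start date. Let each be missing with probability m, among N = 1,500.

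- Gaps all in the same patients: m × 1,500 = 15 (m = 1%) to 45 (m = 3%).
- Independent gaps, 1 − (1 − m)^6:
  - m = 1%: 5.9%, or 88 patients
  - m = 2%: 11.4%, or 171 patients
  - m = 3%: 16.7%, or 251 patients
- Finished-review reading with a full register: near 0.

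**Effect on an estimate**

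Let a share q be dropped, and let the kept patients show 50% event-free.

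- Worst case, (1 − q) × 0.5 to (1 − q) × 0.5 + q: 47.5% to 52.5% for q = 5%; 45% to 55% for q = 10%.
- Dropped patients at h times the hazard of the kept, (1 − q) × 0.5 + q × 0.5^h with h = 2 or 0.5: 48.8% to 51.0% for q = 5%; 47.5% to 52.1% for q = 10%.
- Median. The kept patients' median is set at 20.0 months, the real-world PFS figure for palbociclib plus letrozole in protocol section 7, so λ = ln 2 / 20.0. Solve (1 − q)·exp(−λt) + q·exp(−hλt) = 0.5:
  - q = 5%: 19.3 months (h = 2) to 20.6 months (h = 0.5)
  - q = 10%: 18.6 months (h = 2) to 21.3 months (h = 0.5)

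**ToT, separate and secondary**

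Kaplan-Meier needs an event or censoring time for every patient. Without a stated date, 31 December 2020 and 01 May 2022 are both open. There is also no rule for a patient who died or moved to another treatment without a recorded stop date.

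**The case against.** The strongest defence is that complete simply means finished. The register is built by systematic review of all electronic patient records on a standard form. Coverage was expected by the end of 2021, before data collection starts on 01 February 2022. Protocol 9.1 says that the needed data exist in structured form at study start, and protocol 9.6 calls them high quality and ready to analyse. On that view almost nobody is lost. This stands as a plausible reading, and it is why the lower end of the range is near 0. It does not define the word, deal with gaps inside finished records, or give a count showing that few were lost.

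Second, every missing rate and hazard ratio above is an assumption, the resulting shifts are modest, and no hypothesis is tested. This stands, and it limits the severity.

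Third, the no-selection-bias sentences are rationale text about national coverage, and protocol 9.7 lets the SAP modify the protocol. This weakens the conflict with the protocol. It does not touch the conflict inside the SAP, between section 6 and its own exclusion criteria.

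A reader might go further and infer that patients still on palbociclib are dropped for want of a stop date, which would shorten ToT greatly. The documents do not support that. Kaplan-Meier for ToT implies that ongoing patients are censored; only the date and the rule for unrecorded stops are missing.

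**Conclusion.** The point holds as a should-fix. SAP section 6 sets an undefined, unlisted exclusion. It contradicts the SAP's statement that there are no exclusion criteria and its claim that all patients are included, and nothing planned would show how many patients it removes. The conclusion that missing-value handling is irrelevant rests on that undefined condition.

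The size cannot be derived from the documents. Under the assumptions shown, the loss runs from near 0 to 251 of 1,500, and a 5% to 10% loss moves a 20.0-month median to somewhere within about 18.6 to 21.3 months. The median calculation assumes exponential times and a twofold hazard difference either way. It would be too strong to say that the primary results are materially biased: no missing-data rate is given, and one reasonable reading loses almost nobody.

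The absent ToT censoring date is a real gap in an endpoint definition, but it is separate and the severity does not rest on it.

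**What to change.** Replace SAP section 6 as follows:

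- Analyse all patients who meet the inclusion criteria.
- Show missing baseline items as unknown in Tables 2 and 3.
- Add an attrition table: identified, eligible, excluded with reason, and lacking a usable index, start or stop date.
- If a completeness restriction is kept, define it only by baseline variables or by finished record review, list it as an exclusion criterion, report the number excluded, and qualify the statements that all patients are included without selection bias.

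Separately, for ToT:

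- State a censoring date.
- Censor at that date patients with no recorded stop date, death or subsequent treatment.
- Where death or subsequent treatment is recorded but no stop date is, state whether that registered date ends or censors ToT, report the number of such patients, and add one sensitivity analysis.
- Use only what the register already holds, since protocol 9.1 rules out further collection. Table 1 lists the death date and the subsequent-treatment variables but does not name a date for the latter, so confirm that one exists before relying on it. Table 1 has no variable for a last date known to be on treatment, so the rule should not depend on one.

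The cost is SAP wording, one attrition table, some unknown rows and one sensitivity analysis. A protocol amendment may be needed if the ToT rule counts as a major change to a primary endpoint under protocol 9.7.
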